## **5.2 Protocol deviations**

Important protocol deviations will be identified and classified by the deviations types listed in the IPD document.

A listing of all IPDs will be presented for all subjects in the RS and will include the deviation type and description.

The number and percentage of subjects with IPDs will be summarized by treatment group and for all subjects for each deviation type, based on the RS. This summary will be repeated for the FAS (if this analysis set is different to the RS).

## 6 DEMOGRAPHICS AND OTHER BASELINE CHARACTERISTICS

### 6.1 Derivation of variables

#### 6.1.1 Calculation of body mass index

The body mass index (BMI) in kg/m^2 is calculated based on the height (in m) and the weight (in kg) using the following formula:

$$BMI = \frac{Weight}{(Height)^2}$$

The BMI will be automatically derived by and recorded on the electronic case report form (eCRF).

#### 6.1.2 Classification of age categories

Age will be classified into categories based on requirements for European Union Drug Regulating Authorities Clinical Trials (EudraCT) and clinicaltrials.gov reporting.

For the EudraCT reporting, the categories will include:

- 18 to <65 years
- 65 to <85 years
- ≥85 years

For the clinicaltrials.gov reporting, the categories will include:

- ≤18 years
- 19 to <65 years
- ≥65 years

#### 6.1.3 Duration of disease

The duration of disease will be calculated as follows and will be presented in years to 1 decimal place:

$$Duration = Date of Screening - Date of Diagnosis$$

In the event that the date of diagnosis is incomplete, it will be imputed to the most recent feasible date (ie, the imputed date must be before the date of Screening):

- If only the day is missing, it will be imputed to the last day of the known month
- If the day and month are missing, it will be imputed to December 31 in the known year
- If the date of diagnosis is completely missing or if the imputed date is not feasible, the duration of disease will not be calculated

### 6.2 Demographics

A by-subject listing of Baseline demographic characteristics will be presented by treatment group. This will include the year of birth (if available), age (in years), sex, race, ethnicity, height (in cm), weight at Screening (in kg) and body mass index (BMI) for all subjects screened. The

age and BMI will be obtained from the electronic case report form (eCRF) and will not be re-calculated for the reporting of demographic data.

All Baseline demographic characteristics (with the exception of year of birth) will be summarized by treatment group and for all subjects based on the SS. The summary of age will include descriptive statistics and categorical summaries, the latter based on requirements for EudraCT and clinicaltrials.gov reporting. This summary will be repeated for subjects in the SS who were randomized in the PET-MRI/CT substudy. Childbearing potential will be listed for the SS.

### 6.3 Other Baseline characteristics

The following Baseline disease characteristics will be presented in a by-subject listing for the SS:

- Duration of disease (as calculated in [Section 6.1.3](#)), including confirmation of sacroiliac joint X-ray and the date on which the sacroiliac joint X-ray was performed
- hs-CRP
- BASDAI score
- PGADA
- ASDAS
- ASDAS disease activity states (ASDAS-ID, ASDAS-Moderate Disease activity [ASDAS-MD], ASDAS-High Disease activity [ASDAS-HD] and ASDAS-Very High Disease activity [ASDAS-vHD])
- BASFI score
- Total and nocturnal spinal pain NRS
- PhGADA
- Total HADS-A and HADS-D scores

The calculation of Baseline ASDAS and the classification of the ASDAS disease activity states will be based on the Baseline BASDAI, PGADA and hs-CRP values. The Baseline for each of the variables listed above is defined in [Table 3-1](#).

Baseline disease characteristics will be summarized using descriptive statistics by treatment group and for all subjects based on the SS. This summary will be repeated for subjects in the SS who were randomized in the PET-MRI/PET-CT substudy and will also include summary statistics for  $SUV_{auc}$  in the SIJ and spine at Baseline derived from the PET-MRI/PET-CT scans performed at Screening.  $SUV_{auc}$  values for each of the PET-positive lesions identified in the SIJ and spine will be pooled across subjects and across the SIJ and anatomical locations in the spine for the purpose of this summary. In addition, the maximum  $SUV_{auc}$  value across the SIJ and spine for each subject at Baseline will be summarized.

The above Baseline disease characteristics will be listed for the SS.

Subject lifestyle details (alcohol use, smoking history and caffeine use) will be listed, based on the SS.

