### 3.5.8 PET Per-Protocol Set

The PET Per-Protocol Set (PET-PPS) will consist of all randomized subjects who receive at least 1 dose of the IMP and have evaluable PET-MRI or PET-CT scan data at Baseline and at least 1 of the post-Baseline assessments.

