Another reader who has not been involved in the visual identification of the PET-positive lesions, either as a primary reader or an adjudicator, will then draw volumes of interest (VOIs) on the pre-identified PET-positive lesions. In the case that no PET-positive lesions have been identified for a subject, then the final review step to draw VOIs will not occur. Efficacy PET-MRI/PET-CT review will occur provided that an acceptable PET-CT or PET-MRI scan is available and that PET-positive lesions were identified on the previous scan (for the Week 12 and Week 48 visits). During the PET-positive lesion VOI review, the independent reviewer will perform a quantitative assessment in ACCURATE and record the standard uptake values of  $^{18}\text{F}$ -fluoride in VOIs, corrected for both body weight and individual integrated whole blood activity concentration (SUVauc) for each PET-positive lesion identified during the PET-positive lesion identification review.

Data from the visual identification of PET-positive lesions and the results of the quantitative VOI review (i.e. SUVauc) will be listed, for each independent reader and adjudicator (if applicable), for each anatomical location in the spine, and for each side of the SIJ, by treatment group and visit for subjects in the SS who were enrolled into the PET-MRI/PET-CT substudy.

No formal statistical modelling of the PET-MRI/PET-CT imaging data will be performed for this substudy; only summaries will be presented together with 95% CIs for mean values, as applicable.

The summaries described below based on the visual identification of PET-positive lesions will include the final assessment data, ie, if adjudication was performed, then the adjudicated data will be summarized, otherwise data from one of the primary reviewers will be summarized.

All summaries will be presented for the PET-PPS.

Since the attenuation correction and quantification is variable in PET-MRI scans, PET-MRI imaging data will be listed but will not be aggregated with the PET-CT imaging data in the summaries.

Due to the predicted sparseness of the number of PET-positive lesions in each of the individual anatomical locations of the spine, data will be pooled as follows for the purpose of some of the summaries:

- In the SIJ and spine overall (across the SIJ and all anatomical locations in the spine);
- In the SIJ overall (across both sides), and split by Left and Right side;

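### The Baseline SUVauc summary in SAP 6.3 does not exclude PET-MRI, although SAP 8.3.6.2 keeps PET-MRI out of summaries with PET-CT

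*SAP*

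**What the plan says.** SAP 6.3 (Other Baseline characteristics) presents Baseline disease characteristics by treatment group and overall on the Safety Set (SS), then adds a substudy version: "This summary will be repeated for subjects in the SS who were randomized in the PET-MRI/PET-CT substudy". The substudy version also carries SUVauc statistics "in the SIJ and spine at Baseline derived from the PET-MRI/PET-CT scans performed at Screening". For these, "values for each of the PET-positive lesions identified in the SIJ and spine will be pooled across subjects and across the SIJ" and the spinal locations. Each subject's maximum SUVauc is summarized as well. The section does not split by modality, does not exclude PET-MRI and does not point to 8.3.6.2.

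SAP 8.3.6.2 (Efficacy assessment) takes a different position on the same kind of data. It gives a reason, "Since the attenuation correction and quantification is variable in PET-MRI scans", and then a rule: "PET-MRI imaging data will be listed but will not be aggregated with the PET-CT imaging data in the summaries". On the analysis set it says: "All summaries will be presented for the PET-PPS". SAP 3.5.8 admits to that set treated, randomized subjects who "have evaluable PET-MRI or PET-CT scan data at Baseline and at least 1 of the post-Baseline assessments".

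Protocol 9.11 allows either a PET-MRI or a PET-CT system. Protocol 3.3 classes bone formation as an exploratory objective.

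**The concern.** The SAP gives a measurement reason for not combining the two modalities, and that reason concerns the scans themselves, so it applies at Baseline as much as at Week 12 or Week 48. The Baseline table in 6.3 nevertheless has no such restriction. Read literally, it puts PET-MRI and PET-CT lesion values into one mean and one standard deviation per arm.

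Readers use a Baseline table to judge whether the arms started alike. If one arm happened to have more PET-MRI subjects, a modality effect could be taken for a difference in Baseline bone formation, and the table would not show the cause. No test, decision rule or primary result depends on it.

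**Working it through.** The plan states no figure on this point, so there is none to reproduce. The check is a comparison of the two sections, followed by how far mixing could matter.

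**1. Side by side**

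| | SAP 6.3 | SAP 8.3.6.2 |
|---|---|---|
| Quantity at Baseline | lesion SUVauc; maximum per subject | lesion SUVauc by visit; maximum per subject by visit |
| Combined over | subjects, SIJ and spine | subjects, for pooled locations that include SIJ and spine together |
| Modality | both named, no restriction | PET-MRI in listings only |
| Analysis set | SS, substudy subjects | PET-PPS |

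The quantities are the same and the modality row differs. Both texts are current. The SAP's own record of its Amendment 3 shows both sections being revised then, so neither is left over from an older plan.

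**2. How mixing could create an apparent difference**

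Let *p* be the share of an arm's lesions read on PET-MRI. Let *C* and *M* be the mean SUVauc that PET-CT and PET-MRI would give for lesions of the same true activity. Then

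arm mean = (1 − *p*)·*C* + *p*·*M*

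With identical true activity in both arms,

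apparent difference = (*p*_BKZ − *p*_CZP)·(*M* − *C*)

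This is zero if there is no PET-MRI, if the PET-MRI shares are equal, or if the two modalities agree on average. In the last case, mixing mainly widens the spread. The documents give no value for *p*, *C* or *M*.

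**3. Why a chance imbalance is plausible**

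- SAP 2.3 plans about 25 substudy subjects. At 2:1 this is 25 × 2/3 ≈ 17 on bimekizumab and 25 × 1/3 ≈ 8 on CZP.
- Protocol 7.10 names no stratification by modality.
- As an assumed example, two PET-MRI subjects would be 2/8 = 25% of the CZP arm, or 2/17 ≈ 12% of the bimekizumab arm.
- The lesion summary counts lesions rather than subjects. One subject can contribute up to 24 × 8 = 192 spinal locations plus 2 SIJ sides, 194 in all, so a few PET-MRI subjects could supply a larger or smaller share than their number suggests.

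**4. How many subjects could be affected**

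Let *m* of 25 subjects be scanned by PET-MRI (an assumption). Section 6.3 then draws on up to 25 subjects, and the PET-CT summaries in 8.3.6.2 on up to 25 − *m*: 25 and 25 for *m* = 0; 25 and 20 for *m* = 5; 25 and 13 for *m* = 12. These are upper limits, because a subject with no PET-positive lesion has no SUVauc and the PET-PPS also requires a post-Baseline scan.

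**The case against.** The strongest reply is that 6.3 never says the modalities are combined. It speaks of combining over subjects and locations, and the paired term for the scans is the SAP's usual label for the whole substudy; it appears in Table 3-1 and in 8.3.6.2 itself. Since the rule in 8.3.6.2 rests on a property of PET-MRI data, its reference to summaries could be taken to cover 6.3 too. On that reading only a cross-reference is missing.

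Part of this stands. The intention may well have been to exclude PET-MRI everywhere. But the rule sits in the efficacy section, ahead of the summaries described there, while 6.3 names both scan types, restricts neither and refers nowhere. The text has to settle this, not the programmer.

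A reader might infer more, and four such readings should be set aside:

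- **That the SS in 6.3 conflicts with the PET-PPS in 8.3.6.2.** It does not. The characteristics summaries in SAP Section 6 routinely use the SS, repeated for substudy subjects. Different denominators for a Baseline table and an efficacy table are ordinary.
- **That a PET-PPS Baseline table is missing.** Section 8.3.6.2 already provides one. Its by-visit summaries of lesion and maximum SUVauc include Baseline, use the PET-PPS and do not aggregate PET-MRI with PET-CT.
- **That the SAP regards PET-MRI values as unreliable, or as too variable to use.** It says only that attenuation correction and quantification vary.
- **That the correction would make 6.3 agree with the change tables.** It would not. The analysis sets would still differ, and a lesion's change needs a value at both visits.

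**Conclusion.** The modality inconsistency is real and minor. As written, 6.3 allows PET-MRI and PET-CT values to be combined in a by-arm Baseline summary, while 8.3.6.2 keeps them apart for a stated measurement reason.

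The conclusion assumes that at least one substudy subject has PET-positive lesions on PET-MRI at Screening. The protocol permits this, but the documents do not say how often it occurs. If all scans are PET-CT, the effect is zero. No PET-MRI share and no size of distortion can be drawn from the documents; the counts in the working are illustrations only.

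The consequence is limited to one descriptive table. SAP 8.3.6.2 plans no formal modelling of the imaging data, and the primary analysis is untouched. SUVauc is also listed by arm and visit, so the individual values remain available, but the summary itself would not reveal a mixture.

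**What to change.** In SAP 6.3, state that the Baseline summaries of lesion SUVauc and of maximum SUVauc per subject use PET-CT scans only, that PET-MRI values appear in the listings only, and that 8.3.6.2 governs the handling of PET-MRI. Keep the SS as the analysis set.

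The cost is one clause and one table filter. No new data, listing or table is required, since 8.3.6.2 already lists SUVauc for SS subjects in the substudy. SAP Section 1 requires a SAP amendment for changes to analysis definitions before database lock, so the clause can go into the next one.

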## **6.4 Medical history and concomitant diseases**

Medical history (except for AS) will be listed for the RS and summarized for the SS by treatment group and for all subjects, MedDRA® system organ class (SOC) and preferred term (PT). The reported term will be included in the listing. The summary will include the number and percentage of subjects and will be sorted alphabetically by SOC and by descending incidence of PT within each SOC, based on the 'All Subjects' column. This summary will be repeated for subjects in the SS who were randomized in the PET-MRI/CT substudy. A glossary of all medical history conditions will be presented for the RS including the SOC, PT and reported term.

Procedure history will be listed separately for the RS by treatment group for previous procedures relating to AS and previous procedures not relating to AS. Concomitant medical procedures performed during the study will be listed for the RS.

## **6.5 Ankylosing spondylitis history**

Date of initial diagnosis of AS and the date that AS symptoms first started will be listed.

## **6.6 Prior and concomitant medications**

Prior and concomitant medications (Section 6.6.1 and Section 6.6.2) will be listed for the RS by treatment group and subject, and summarized for the SS by WHODD Anatomical Main Group (Level 1), Pharmacological Subgroup (Level 3) and PT. The reported term will be included in the listing, together with flags to identify AS, rescue and prohibited medications, respectively. The flags for prohibited, AS and rescue medications will be confirmed and documented at the final DEM.

Prohibited medications will be listed separately.

Separate summaries will be presented for prior medications and concomitant medications and these will be presented by treatment group and for all subjects. Prior medications which continued into the study period are also classified as concomitant and are included in both summaries.

Separate summaries will be presented for the following, identified using WHODD Anatomical Main Group codes, the indication recorded on the eCRF and medical review of the recorded data:

- Prior and concomitant AS medications
- Rescue medication during study

All AS medications and rescue medication given during the study will be identified via medical review of the concomitant medications and confirmed at the DEMs prior to unblinding.

These summaries will be repeated for subjects in the SS who were randomized in the PET-MRI/PET-CT substudy.

All tabulations will be sorted alphabetically by Level 1 term, alphabetical Level 3 term within Level 1 and decreasing frequency of PT in the 'All Subjects' column.

A glossary of all prior and concomitant medications will be presented for the SS including the Anatomical Main Group (Level 1), Pharmacological Subgroup (Level 3), PT and reported Term.

Any medications with partially missing dates and/or times will be handled as described in [Section 4.2.5](#) to classify them as prior or concomitant.

### **6.6.1 Prior medication definition**

A medication with a start date that is prior to the date of first dose of IMP will be classified as a ‘prior medication’.

### **6.6.2 Concomitant medication definition**

A medication with a start date that is on or after the date of first dose of IMP will be classified as a ‘concomitant medication’.

Any medication that started prior to the first dose of IMP and continued after will be classified as both prior and concomitant. Such medications will therefore be counted in the tabulations for both prior and concomitant medication.

## **7 MEASUREMENTS OF TREATMENT COMPLIANCE**

During the Treatment Period of this study, IMP will be administered in the clinic and compliance will be determined at the visit by study personnel.

The number of injections administered at each visit will be included in the listing of IMP administration as specified in [Section 11.1](#).

In addition, the percentage of planned injections administered will be calculated and presented on the listing.

This will be calculated as follows:

$$\% \text{Planned Injections Administered} = \frac{\text{Total Number of Injections Received}}{\text{Total Number of Planned Injections}} \times 100$$

where the planned number of injections for subjects who have completed the study is 14 for the Treatment Period and 16 for the Treatment Period (total of 30 injections). For subjects who have discontinued prematurely from the study, the planned number of injections will be the number of planned injections up to the date of discontinuation.

Any deviations from the planned dosing schedule will be addressed at the DEMs (including evaluation of any impact on the statistical analysis) and described in the CSR. No formal calculations of compliance will be presented as all IMP will be administered on site.

## **8 EFFICACY ANALYSES**

### **8.1 Primary efficacy variable**

#### **8.1.1 Derivation of the primary efficacy variable**

The ASDAS will be calculated based on individual component assessments of spinal pain, duration of morning stiffness and peripheral pain/swelling from the BASDAI together with the PGADA and hs-CRP values at the corresponding visit.

#### **8.1.1.1 Bath Ankylosing Spondylitis Disease Activity Index**

The BASDAI is the most commonly used instrument to measure the disease activity of AS from the subject’s perspective. The BASDAI is a validated self-reported instrument which consists of

6 questions scored on a 0 to 10-unit horizontal numeric rating scale (NRS) to measure the severity of the 5 major symptoms: fatigue, spinal and peripheral joint pain and swelling, enthesitis, and morning stiffness (both severity and duration, respectively) over the last week.

Questions 2, 3 and 6 of the BASDAI are used in the calculation of ASDAS.

Question 2 asks [REDACTED]

Question 3 of the BASDAI [REDACTED]

Question 6 of the BASDAI [REDACTED]

[REDACTED] (Section 8.1.1.4).

The full BASDAI questionnaire is shown in [Section 14.1](#).

#### **8.1.1.2 Patient's Global Assessment of Disease Activity**

Subjects will provide a global assessment of their disease activity in response to the question “How active was your spondylitis on average during the last week?” using a NRS where 0 is “not active” and 10 is “very active”.

#### **8.1.1.3 High-sensitivity C-reactive protein**

Blood will be collected for the measurement of hs-CRP.

#### **8.1.1.4 Calculation of Ankylosing Spondylitis Disease Activity Score**

Each of the individual component assessments described above in [Section 8.1.1.1](#), [Section 8.1.1.2](#) and [Section 8.1.1.3](#) are multiplied by a validated factor (van der Heijde et al, 2005) as listed below:

- 0.121 x Total spinal pain (BASDAI Question 2 result)
- 0.058 x Duration of morning stiffness (BASDAI Question 6 result)
- 0.110 x PGADA
- 0.073 x Peripheral pain/swelling (BASDAI Question 3 result)
- 0.579 x (natural logarithm of the hs-CRP [mg/L] + 1)

The results of these individual calculations or weighted components are then summed to obtain the ASDAS.

Handling of missing data and values of hs-CRP that are below 2 mg/L will be handled as described in [Section 4.2.1.1](#).

ASDAS will be calculated at Baseline and at each post-Baseline visit per the schedule of assessments in the protocol.

The primary efficacy analysis will be based on the change from Baseline in ASDAS at Week 12.

## 8.1.2 Primary analysis of the primary efficacy variable

The primary efficacy analysis of the primary efficacy variable will be based on the PPS.

The primary efficacy analysis is the comparison of the change from Baseline in ASDAS at Week 12 in the BKZ treatment group versus the CZP treatment group in the PPS.

### 8.1.2.1 Bayesian modeling

The primary statistical analysis of the primary efficacy variable at Week 12 will be conducted following a Bayesian paradigm. The Bayesian analysis will be performed using a linear regression model including treatment group and Baseline ASDAS (mean centered using the overall ASDAS mean). The model will be parameterized such that the effect of CZP is represented by the intercept parameter whilst the effect of BKZ is additive to this. An informative prior will be used for the model for the intercept coefficient which, in the primary model, is equal to the mean change from Baseline in ASDAS in the CZP group when the centered Baseline mean is zero ( $\beta_{CZP} \sim \text{Normal} [-1.78, \text{var}=0.0605]$ ). Vague priors will be used for the other model coefficients, ie, centered Baseline coefficient and additive effect of BKZ.

Proof of Concept (PoC) will be declared if the posterior probability of a positive difference in the mean change from Baseline in ASDAS at Week 12 between the CZP and BKZ treatment groups (CZP-BKZ) is 0.975 or greater (ie, the lower bound of the 95% credible interval of the difference between treatment groups in the mean change from Baseline in ASDAS is zero or greater).

The model to be used is as follows:

$$y_i \sim \beta_{CZP} + \beta_{bl}x_{i,bl} + \beta_{BKZ}x_{i,BKZ}$$

Where  $i$  indexes the  $i = 1, \dots, N$  subjects,  $y_i$  is the change from Baseline in ASDAS at Week 12 for subject  $i$ ,  $x_{i,bl}$  is the centered Baseline ASDAS for subject  $i$ ,  $x_{i,BKZ}$  is a variable equal to 1 if subject  $i$  was randomized to the BKZ group and 0 if not,  $\beta_{CZP}$  is the model intercept,  $\beta_{bl}$  is the coefficient for the centered Baseline ASDAS, and  $\beta_{BKZ}$  is the additive effect of BKZ in addition to the effect of CZP.

The prior distributions for the model parameters are:

$$\begin{aligned}\beta_{CZP} &\sim N(-1.78, \sigma_{CZP}^2 = 0.0605) \\ \beta_{bl} &\sim N(0, \sigma_{bl}^2 = 10^6) \\ \beta_{BKZ} &\sim N(0, \sigma_{BKZ}^2 = 10^6)\end{aligned}$$

where the prior for  $\beta_{CZP}$  is worth approximately 20 subjects (Section 2.4). The sample sizing for this study was based on the assumption that  $\sigma^2=1.1$  which was based on the CZP data available from a single internal study (Section 8.1.2.2).

In addition to the primary Bayesian analysis where subjects with missing data will be excluded from the analysis, a supportive analysis based on imputed or predicted values for the change from Baseline in ASDAS at Week 12 will be performed.

Predicted Week 12 values for the subjects who do not have ASDAS values for the Week 12 visit will be obtained from a Mixed Model Repeated Measures (MMRM) analysis. The model will include treatment group, visit and the treatment group by visit interaction as fixed effects (visit as a categorical variable) and Baseline ASDAS as a continuous covariate. Subject-level random intercepts and slopes (visit as a continuous variable) will be included in the model and a 2 x 2

unstructured covariance matrix for these random effects will be used, along with a simple covariance structure for the within-subject errors.

If the model fails to converge then the simpler subject-level model including the intercept as only random effect will be fitted. If there are still problems with convergence and/or if the estimated response covariance matrices (random effects and response) are not positive definite, then alternative models will be considered, eg, allowing the random effects covariance parameters to be unbounded, or modelling the response covariance structure without using random effects.

The combination of observed and predicted values of change from Baseline in ASDAS at Week 12 obtained from the MMRM will then be modelled as the response variable in this supportive Bayesian analysis.

